5.6.1.4. Vaccine efficacy by variant

Upon availability of viral genome sequencing data for molecularly confirmed COVID-19 cases and upon the condition that the proportion of sequenced cases is comparable between the active group and the placebo group, vaccine efficacy for the efficacy endpoints defined in section 5.4 and section 0 above will be evaluated by variant (as defined in section 5.8.2.6.) as well as those with no variant of interest.

For each efficacy endpoint and each variant the following analysis will be done:

Endpoints identified with a specific variant will be included in the analysis. Subjects with an endpoint for which the variant is missing or identified to be different, are not included as a case. Their follow-up time is included up to the onset of the case with the missing or other variant.

The time to onset of the first occurrence of molecularly confirmed COVID-19 for a given variant will be graphically summarized using Kaplan-Meier methods for each group by variant, by variant within a country. Vaccine Efficacy (*VE*) and the associated confidence interval will be calculating according to the methodology as explained in Appendix 8. If less than 6 cases observed for a given variant, or for a given variant within a country, no *VE* calculation will be done and the numbers only tabulated.

The above analysis will be repeated by country. The analysis will be done based on cases with onset after Day 14 after double-blind vaccination (PP-set, seronegative subjects), on cases with onset after Day 28 after double-blind vaccination (PP-set, seronegative subjects) and cases with onset after Day 1 double-blind vaccination (full-analysis set).

The analysis will be repeated regardless of serostatus.

5.7. (Other) Safety Analyses

Following information will be collected for:

Participants in the Safety Subset:

- Solicited local and systemic adverse events (AEs) for 7 days after double-blind vaccination
- Unsolicited AEs for 28 days after double-blind vaccination

All participants in the FAS during the entire study:

- Serious adverse events (SAEs) and MAAEs leading to study discontinuation after vaccination
- AESI (AE of Special Interest)

All participants in the FAS during the first 6 months:

- Medically-attended adverse events (MAAEs) after vaccination

Safety analyses will be performed on the FAS. No formal statistical testing of safety data is planned. Safety data by double-blind vaccination group will be analyzed descriptively. Specific safety analyses will be performed on the Safety Subset. All safety analyses will be tabulated by treatment group (active vaccine, placebo) according to the as-treated principle. All safety analyses will be presented overall and by age and comorbidity (with/without) strata. The main age strata for reporting purposes are ≥ 18 to < 60 years of age and ≥ 60 years of age. In addition, safety data will be analyzed by treatment group and participant seropositivity status at screening.

For the double-blind phase, the safety data up to the unblinding date will be presented separately for the Ad26.Cov 2 double-blind group and the placebo double-blind group (Analysis I). Safety data after the unblinding date but before the open label vaccination date are listed separately.

Additionally, safety data will be pooled for all subjects that received Ad26.Cov 2 (in the double blind phase or in the open label phase) from the start of their Ad26.Cov 2 vaccination to the end of the trial (Analysis II): unsolicited AEs up to day 28, SAEs and MAAEs leading to discontinuation during the entire study, MAAEs until 6 months after last vaccination, AEs of special interest and AEs of interest during the entire study. All tables will be presented by phase.

The safety data from subjects that were unblinded and who received a vaccine outside the study will be tabulated separately.

Subjects that took another COVID-19 vaccine before being unblinded are excluded from the safety tables from the moment they received the other vaccine. The safety data from those subjects after they received the other vaccine are listed separately.

Denominator for the percentages is the number of participants in the considered population and phase for a certain regimen (incidence per 100 participants/phase).

Continuous variables will be summarized using the following statistics, as appropriate: number of observations, arithmetic mean (mean), 95% CI for the mean, standard deviation (SD), median, quartiles (Q1 and Q3), minimum and maximum. Frequencies and percentages (one decimal place) will be generated for categorical variables. No formal comparisons between groups will be provided.

Other exploratory or sensitivity analyses may be performed in addition to the analyses described below on an ad-hoc basis.

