5.5.4.5. AUC viral load

To compare VL-AUC after infection between the active and placebo groups, the exact Wilcoxon Rank Sum test will be performed.

Values below the LLOQ will be imputed with 1 when detected and with 0 when not detected.

These imputations will be used when calculating the AUC based on equation (1). In addition, in case some observations are missing at the first timepoint after infection and/ or the last timepoint after challenge, missing values should be imputed with 0. No other missing values will be imputed.

AUC-VL values will be descriptively summarized (mean, median, SD, SE, range) by randomized group and COVID-19 severity (all symptomatic infections, mild, moderate to severe/critical).

Individual profiles of viral load over time and $\log_{10}[\text{viral load}]$ over time since onset of a COVID-19 episode will be summarized by randomized group and severity of COVID-19.

The vaccine efficacy against AUC-VL will be estimated through the geometric mean ratio of AUC-VL with associated 95% confidence interval.

As the comparison of the AUC VL after infection between the active and placebo groups is based on post-randomization groups, this analysis may not assess the causal effect of the vaccine on viral load. A sensitivity analysis as described by Gilbert et al. (2003) will be carried out. In this sensitivity analysis, a logistic selection bias model is employed to define a causal estimator for the vaccine effect on viral load. The unknown slope (b) of this logistic model determines the amount of selection bias; b is varied over a plausible range of values. For each value of b , a non-parametric estimate of the causal vaccine effect is calculated. A confidence interval and p-values for the appropriate hypothesis of interest are obtained by bootstrap. If $b < 0$, there is a selection bias towards a lower viral load in the vaccine group as compared to the placebo group. When $b = 0$, no selection bias is assumed. The hypothesis of interest is the one-sided hypothesis of a reduction of the viral load. Therefore, values of $b \leq 0$ will be considered (from -5 to 0 in steps of 0.01). The estimate of the causal vaccine effect with its $100*(1-2*\alpha)$ % confidence interval and the p-value for the one-sided hypothesis of a viral load reduction in the vaccine group will be plotted against the assumed value of b .

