5.8.2.6. SARS-CoV-2 viral genome sequence analysis

SARS-CoV-2 viral genome sequence analysis will be performed using Next Generation Sequencing (NGS) using the SWIFT Biosciences to evaluate the presence of polymorphisms and variations at the amino acid level.

Sequence results will be presented only for the spike protein and is focused on a predefined list of amino acid positions of interest. Data are transferred as the consensus sequence from the sample (i.e. no minority variants or mutation frequencies are transferred for this analysis). A separate virology report will be prepared.

Time Points and Samples

Samples for viral sequencing are taken throughout the T&E schedule. An attempt is made to sequence the sample closest to the onset of symptoms, but sequencing is triggered at the discretion of the virologist considering the SARS-CoV-2 viral load levels and the limitations of the sequencing assays.

Definitions

Polymorphisms, ie genetic variations, are defined as amino acid changes from the SARS-CoV-2 Wuhan-Hu1 Reference Sequence.

Wild type: If at certain position the amino acid in the participant sequence matches the reference sequence, that is no genetic variation is present at that position, the virus is considered to be wild type at that position.

Parameters to Analyze

The following parameters will be analyzed:

Number (%) of participants with a SARS-CoV-2 variant with a specific substitution (“amino acid level”, see below).

Number (%) of participants with a SARS-CoV-2 variant with a specific substitution profile (“variants”, see below)

Positions & Genetic Variations of Interest

Amino acid level:

In the SARS-CoV-2 spike protein, based on changes in the N-terminal or receptor binding domains, and changes observed in naturally occurring variants

- S13I, L18F, T20N, P26S, 69del + 70del, D80A, L98F, D138Y, Y144del, W152C, R190S, D215G, L242H, 242del + 243del + 244del, R246I, K417N, K417T, N439K, V445A, L452R, Y453F, S477N, S477R, E484K, N501Y, A520S, A570D, D614G, H655Y, P681H, A701V, T761I, S982A, T1027I, D1118H

Variants (lineage-WHO label-defining mutations):

- B.1.1.7 – Alpha - H69del, V70del, Y144del, N501Y, A570D, D614G, P681H, T716I, S982A, D1118H
- B.1.351 – Beta – K417N, E484K, N501Y, D614G, A701V
- B.1.617.2/AY.1/AY.2 – Delta – L452R, T478K, D614G, P681R
- B.1.427/429 – Epsilon – W152C, L452R, D614G
- B.1.525 - Eta - A67V, H69del, V70del, Y144del, E484K, D614G, Q677H, F888L
- P.1 – Gamma - K417T, E484K, N501Y, D614G, H655Y

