- B.1.526 – Iota - L5F, T95I, D253G, D614G, E484K, A701V
- B.1.617.1 – Kappa - G142D, E154K, L452R, E484Q, D614G, P681R
- C.37 – Lambda - R246del, S247del, Y248del, L249del, T250del, P251del, G252del, D253N, L452Q, F490S, D614G, T859N
- P.3 – Theta - L141del, G142del, V143del, A243del, L244del, E484K, N501Y, D614G, P681H, E1092K, H1101Y, V1176F
- P.2 – Zeta - E484K, D614G, V1176F (and not P.1, not P.3)
- B.1.621 - T95I, Y144T, Y145S, ins145N, R346K, E484K, N501Y, D614G, P681H, D950N
- C.36.3 - W152R, R346S, L452R, D614G, Q677H, A899S
- R.1 - W152L, E484K, D614G, G769V
- B.1.1.519 - T478K, D614G, P681H, T732A
- B.1/B.1.2/B.1.1/B.1.1.214 - D614G (not any other variant)

Additional variants may be added depending upon the epidemiology of SARS-CoV-2 infection.

Analysis Methods

Frequencies and percentages will be presented for the specified parameters. The denominator is the number of subjects with a COVID-19 episode with sequencing data. Summaries will be provided by subgroup and intervention arm.

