6.8. Appendix 8 Statistical Methodology for Poisson Regression

Vaccine efficacy is defined as 1 minus the ratio of the expected incidence rate of cases of COVID-19 in the active group compared to the expected incidence rate in the placebo group.

Vaccine efficacy can be estimated by:

$$\widehat{VE} = 1 - \frac{n_2/N_2}{n_1/N_1} = 1 - \frac{r * n_2}{n_1}$$

Where:

n_2 = number of cases in the vaccinated group

N_2 = follow-up time in the vaccinated group

n_1 = number of cases in the control group

N_1 = follow-up time in the control group

$$r = \frac{N_1}{N_2}.$$

Let $n = n_1 + n_2$ denote the total number of cases. Suppose that $n_i|N_1, N_2 \sim Poisson(N_i p_i)$, $i = 1, 2$, so that $VE = 1 - p_2/p_1$. In this case, conditionally on n and r , n_2 is binomially distributed as $B(n, \pi)$, where $\pi = N_2 p_2 / (N_1 p_1 + N_2 p_2) = (1 - VE) / (r + 1 - VE)$.

Let $q = n_2/n$ denote the proportion of cases in the vaccine group. Then, the vaccine efficacy estimator can be rewritten as:

$$\widehat{VE} = 1 - \frac{n_2}{n} * \frac{r * n}{(n - n_2)} = 1 - \frac{r * q}{(1 - q)}$$

Therefore, there is a monotonically decreasing link between the estimated VE and $q = n_2/n$, the observed proportion of cases in the vaccine group among the total cases, and so rejecting a hypothesis for extreme values of q is equivalent to rejecting that same hypothesis for inversely extreme values of \widehat{VE} .

Given the sequential testing strategy, the confidence interval for the vaccine efficacy will be adjusted accounting for repeated testing. At the primary analysis when the boundary is crossed or at 154 events, the vaccine efficacy estimate will be reported using the estimated VE (as detailed above) at the time of analysis, accompanied with $(1 - 2\alpha^*)\%$ two sided CI, where α^* is the type I error at that time. Using the exact binomial CI for p an (adjusted) exact Poisson regression CI can be constructed (Dragalin et al, 2002; Nauta, 2011). In section X1 the R code to generate the SPRT bounds and to derive the relevant $(1 - 2\alpha^*)\%$ levels is given. The results of the code are presented in [Table 15](#).

1. Section X1: R code SPRT

```

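### VE by variant counts only sequenced cases, so its rate ratio carries the ratio of sequencing probabilities between arms, guarded only by an undefined overall comparability condition

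*SAP*

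**What the plan says.** SAP 5.6.1.4 plans VE by variant for the primary and secondary efficacy endpoints, overall and by country. On endpoints without the lineage in question: "Subjects with an endpoint for which the variant is missing or identified to be different, are not included as a case". On their person-time: "Their follow-up time is included up to the onset of the case with the missing or other variant". The analysis is run "upon the condition that the proportion of sequenced cases is comparable between the active group and the placebo group". No margin, test, time point or level (variant, country, endpoint) is attached to that condition, and 5.6.1.4 names nothing to do if it fails. On sparse data it says: "If less than 6 cases observed for a given variant, or for a given variant within a country, no" VE calculation is made.

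SAP 5.8.2.6 describes how samples come to be sequenced: "sequencing is triggered at the discretion of the virologist considering the SARS-CoV-2 viral load levels and the limitations of the sequencing assays". In the variant frequency tables of the same section, "The denominator is the number of subjects with a COVID-19 episode with sequencing data".

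The estimator is that of Appendix 8: "Vaccine efficacy is defined as 1 minus the ratio of the expected incidence rate of cases of COVID-19 in the active group", relative to the placebo rate.

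SAP 5.5.4.5, on viral load as a secondary endpoint, says of its selection-bias sensitivity analysis: "The hypothesis of interest is the one-sided hypothesis of a reduction of the viral load".

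SAP 5.4.8 also fits models by variant of interest where cases suffice. It sets no comparability condition and does not say how unsequenced cases are handled.

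**The concern.** Censoring cases of another identified lineage is ordinary cause-specific practice and is not at issue. The difficulty is the confirmed, adjudicated endpoint whose lineage is unknown. Treating it as a non-case is harmless for VE only if, within the variant, being sequenced is equally likely in the two arms. The plan gives a reason to doubt this: sequencing depends on viral load, and viral load is something the vaccine is hypothesised to change. For the viral-load comparison itself, 5.5.4.5 prespecifies a sensitivity analysis for post-randomisation selection. Section 5.6.1.4 has none.

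The comparability condition is a weak guard for two reasons. It is undefined, and section 1 says sponsor personnel were unblinded at the primary analysis, so whether VE by variant is reported could be settled by judgement with the arms known. It also looks at the overall share, whereas the bias depends on the share within each variant. At stake is the trial's description of protection against particular lineages, which may be somewhat overstated, or withheld in 5.6.1.4 when sequencing is unbalanced.

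**Working it through.** **Check of the estimator.** The variant section gives no figure. The nearest one using the same Appendix 8 formula is the last row of Table 15: 49 of 154 cases on vaccine. VE = 1 − 49/(154 − 49) = 1 − 49/105 = 0.5333, and P(X ≤ 49) for a binomial with n = 154 and π = 0.7/1.7 is 0.010603. Both match the table.

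**Bias formula.** Let n_v and n_p be the true cases of a variant, and s_v and s_p the probabilities that such a case is sequenced. The expected counted cases are s_v·n_v and s_p·n_p. Follow-up changes little, because person-time is kept to onset. Hence

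reported VE = 1 − (1 − VE) × s_v/s_p.

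If s_v = s_p, reported VE equals true VE whatever the sequencing rate.

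**Size (assumed shares; the SAP gives none).** With s_p = 70%, suppose sequencing requires viral load above a threshold and the vaccine lowers viral load by 0.25 or 0.5 SD. Then s_v = Φ(Φ⁻¹(0.70) − d) = 60.8% or 51.0%.
- 60.8%: ratio 0.869. True VE 50% is reported as 1 − 0.5 × 0.869 = 56.6%; true VE 0% as 13.1%.
- 51.0%: ratio 0.728. True VE 50% is reported as 63.6%; true VE 0% as 27.2%.
- A smaller gap, 75% versus 70%: ratio 0.933. True VE 50% is reported as 53.3%.

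**What the condition would catch, if read as a two-sided 5% Fisher test (an assumption).** A total of 154 cases at VE 60% splits as 110 placebo and 44 vaccine.
- 70% versus 60.8%: the test passes 83% of the time at 110 versus 44 cases, and 64% at 250 versus 100.
- 70% versus 51.0%: the analysis is stopped 57% of the time at 110 versus 44, and 90% at 250 versus 100.

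**Equal overall shares do not protect a variant.** Take 50 placebo cases of each of two lineages, with true VEs of 30% and 70%, so 35 and 15 vaccine cases. Sequence 70% of each lineage on placebo (35 and 35), and 80% and 46.7% on vaccine (28 and 7). Overall shares are 70/100 and 35/50, both 70%. Reported VEs are 1 − 28/35 = 20% and 1 − 7/35 = 80%.

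**Conditioning on viral load repairs the bias in a simple case.** Assume 90% of high-load and 30% of low-load cases are sequenced. Let 70% of 100 placebo cases and 50% of 50 vaccine cases be high-load, so true VE is 50%. Sequenced cases are 63 + 9 = 72 on placebo and 22.5 + 7.5 = 30 on vaccine, so reported VE is 1 − 30/72 = 58.3%. Weighting by 1/0.9 and 1/0.3 gives 70 + 30 = 100 and 25 + 25 = 50, so VE is 50%.

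**The case against.** The strongest reply is that the condition does real work. Simulating a variant with true VE 0 and 50, 100 or 150 placebo cases, plus as many placebo cases of other lineages at VE 60%, the 95% interval wrongly excludes 0 in favour of vaccine in about 6 to 15% of trials at 60.8% sequenced on vaccine and about 20 to 54% at 51.0%. A reader might infer that these are the plan's error rates. They are not, because they ignore the condition. Under the Fisher reading, passing the condition and wrongly excluding 0 occur together in about 2 to 3% and 0 to 2% of trials, against about 1 to 2% with equal shares. Large bias and loss of the analysis are alternatives, not joint outcomes. This stands.

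It is also fair that every sequencing input above is assumed. Section 5.8.2.6 sets no viral-load threshold, cases are swabbed repeatedly, and a lower viral load on vaccine is a hypothesis, not a result.

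A reader might further conclude that sequenced-only VE should be replaced by imputing lineage from country, period, severity and arm. That can introduce bias where there was none. Suppose lineage A is sequenced at 85% and B at 55%, identically in both arms, with 100/100 placebo and 70/30 vaccine cases. The sequenced-only estimate is right: 1 − 59.5/85 = 30% and 1 − 16.5/55 = 70%. Imputing from the within-arm mix gives 121.4/78.6 and 78.3/21.7 cases, hence 35.5% and 72.4%. This too stands: the estimates should be reported side by side, and the model should include viral load.

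**Conclusion.** The concern holds in a limited form. The sequenced-only rate ratio is multiplied by s_v/s_p within the variant, the guard is undefined and applied to the overall share, and 5.6.1.4 plans nothing if it fails. Under the assumed 70% versus 61%, a true VE of 50% is read as about 57%, and a formal test would often miss that gap. At 70% versus 51% such a test would more often than not stop the analysis. The direction rests on the vaccine lowering viral load in cases, and the size rests on shares that the SAP does not give.

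Three stronger readings are not supported. The plan does not estimate efficacy times the chance of being sequenced: it is the rate ratio that is multiplied, and only by a ratio between arms. Lower absolute incidence curves for a variant do not by themselves bias VE. And no confirmatory conclusion is touched: the analysis sits in the tertiary/exploratory section, with confidence intervals and no alpha. Nor would all variant analysis be lost, since 5.4.8 fits variant models without the condition. This is an inexpensive improvement to an exploratory analysis, not a threat to the trial's main result.

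**What to change.** In 5.6.1.4, and for the variant models in 5.4.8:

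- Replace the go/no-go condition with a report of the sequenced share by arm, overall and by country, calendar period and viral load.
- Keep the sequenced-only estimate, and the rule requiring at least 6 observed cases.
- Prespecify beside it an analysis that accounts for unsequenced cases and is run whatever the balance. Use either inverse-probability-of-sequencing weights or multiple imputation of lineage. Base it on a pooled regression model, not fully crossed strata, with viral load, arm, country or region, calendar time of onset and severity. Work on the log rate-ratio scale, and group sparse lineages.

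The data are already planned: 5.5.3 calculates viral load over the episode for all subjects with a molecularly confirmed infection. The cost is SAP wording, some programming and wider intervals. The added analysis assumes that lineage is independent of being sequenced given the variables in the model.

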5.7.1. Adverse Events

5.7.1.1. Definitions

Solicited AEs are used to assess the reactogenicity of the study vaccine and are predefined local (at the injection site) and systemic events for which the participant is specifically questioned, and which are noted by participants in their diary. Unsolicited AEs are all AEs for which the participant is not specifically questioned.

Solicited AEs shown in the tables are extracted from the investigator assessment pages (CE) of the CRF (Safety Subset). For unsolicited AEs, only the AEs within the 28-day period following the double-blind vaccination will be presented in the safety tables (Safety Subset), except for SAEs, MAAEs leading to study discontinuation and AESIs, which will be captured and tabulated in the outputs covering the whole study period and for all subjects in the FAS, and MAAEs (including new onset of chronic diseases) which will be captured and tabulated in the outputs covering the 6 month post double-blind vaccination period (Phases: Post-dose, Follow-up (D30-M6), and Follow-up (M6-W52)) and for all subjects in the FAS.

Solicited administration site symptoms will be by definition considered as related to the study vaccine.

The severity of the AEs will be classified as grade 1 to 4. Solicited events that are graded less than grade 1, are not considered as AE. In case no grades are available, the grading of the solicited events will occur according to the grading list in [Appendix 6](#).

5.7.1.2. Analysis of Adverse Events

Number and percentage of participants with at least one particular AE (unsolicited/solicited) will be tabulated with exact 95% CI, when appropriate. Unsolicited AEs will be summarized by System Organ Class and Preferred Term. Solicited AEs will be summarized by class (administration site, systemic) and preferred term.

For solicited AEs following tables will be provided: summary, by worst severity grade, at least grade 3, related (systemic only), time to onset (in days) and duration (in days) for most frequent events (>5%) and body temperature. Note: Duration is defined as number of days from the start of the event until resolution of the event. The time to first onset is defined as (date of first onset – reference date + 1). The reference date is the start date of the double-blind vaccination period.

For unsolicited AEs following tables will be provided: summary table (including SAE, MAAEs, MAAEs leading to study discontinuation, fatal outcome, and discontinuation), all events, most frequent (>5%), at least grade 3, related and SAE. The proportion of AEs resulting in a medically attended visit (other than routine health maintenance visits) will also be tabulated.

Listings and/or participant narratives will be provided as appropriate, for those participants who die, discontinue study due to an AE, or experience a serious AE.

